### 12.1.2 Supportive Primary Efficacy Analyses

For the purposes of the *USA regulatory clearance pathway*, the number and percentage of people achieving a loss of at least 5% of their body weight by the 6 month time point in the VeSTAL device treatment group will be presented with a two-sided 95% exact binomial confidence interval for the response rate. The criterion for success is that the lower bound of the 95% confidence interval of the response rate in the VeSTAL device group exceeds 50%. The analysis will use the multiple imputation for missing data as primary, with the LOCF and BOCF imputation methods as supportive.

A Fisher's exact test will also be used to compare the response rates in each treatment group and to detect whether the difference between groups is statistically significant. This will be repeated using multiple imputation, LOCF and BOCF methods for missing data. For the multiple imputation-based analysis, the median p-value approach will be used to generate the Fisher's exact test p-value (Eekhout 2017) and the exact confidence intervals described above will be produced using the imputation with a p-value equal to or nearest the median p-value.

In addition, a sensitivity analysis will be performed with the binary weight loss endpoint, to assess the impact of imputing the best and worst case scenarios for the binary response, when the total body weight loss at 6 months is missing. As per section 10.2, a tipping point analysis will also be utilised to demonstrate the level of imputation which changes the significance of the binary weight loss criterion.

No supportive primary efficacy analyses are required for the *EU regulatory clearance pathway*.

Identifier: EXP18020 Clinical Study Identifier: 243973

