### Methods: Primary Aims

For total body weight loss (TBWL) as a continuous measure, we will use a linear regression with TBWL at each time period as the dependent variable and group and other covariates of interest (baseline total body weight, gender, age, study site) as independent variables. As a supportive analysis, we will also a two-sample t-test to examine the differences between the control and active treatment groups at each time period. To assess any longitudinal effects, we will use a linear mixed effects model for weight over time, with fixed covariates for baseline weight, time, group, and a time / group interaction, and a random intercept to account for within-subject correlation. We will use these models to generate two-sided 95% confidence intervals for the difference in mean percent weight loss.

We will calculate exact binomial confidence intervals (95%, two-sided) to determine if the response rate in the treatment group significantly exceeds 50%, with response defined by a loss of at least 5% of their body weight at the 6-month follow-up. As supportive analyses we will also use Fisher's exact test to compare the response rates in each group, and, will consider the use of a logistic regression to control for any other covariates of interest. To investigate possible longitudinal trends, we will fit a logistic mixed effects model, similar to the linear mixed effects model described above.

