## 2.3 Statistical Hypothesis

## 2.3.1 Primary

As the primary efficacy endpoints differ between regulatory clearance pathways, the corresponding statistical hypotheses, tested at 6 months, are also specific to the regulatory pathway.

For both the *USA and EU regulatory clearance pathways*, there will be one statistical hypothesis test to determine the efficacy of the VeSTAL device in comparison to the sham control:

There is no significant difference between the mean percentage weight loss of participants using the VeSTAL device and the sham control, i.e.  $\bar{x}_v - \bar{x}_s >= 0$ , where  $\bar{x}_v$  and  $\bar{x}_s$  are the mean percentage weight loss of participants using the VeSTAL device and sham control respectively.

For the purpose of the *USA regulatory clearance pathway*, the study will be deemed to have met the efficacy criteria if this hypothesis is rejected, and two numerical criteria are achieved:

- The difference between the mean percentage weight loss of participants using the VeSTAL device and the sham control is at least 2% as observed from the confidence intervals, (i.e. equivalent to assessing the hypothesis  $\bar{x}_v \bar{x}_s >= 2$ ).
- The lower bound of the 95% confidence interval of the response rate in the VeSTAL device group exceeds 50%, with response defined as a loss of at least 5% of body weight i.e.  $p_v \frac{1}{2} \left( C_u C_L \right) \geq 50\%$ , where  $p_v$  is the proportion of participants who lose at least 5% body weight using the VeSTAL device.  $C_L$  and  $C_U$  are the lower and upper bounds of the 95% confidence interval.

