#### 5. SAMPLE SIZE CONSIDERATIONS

The primary outcomes are percent total body weight loss from the start of treatment (as a percentage of baseline total body weight), and the proportion of subjects who lose at least 5% of their baseline total body weight. These outcomes will be assessed at the 6-month mark.

Power calculations are based on simulation (for full details see supporting documents EXP18006 Simulation Plan v4.1 and EXP18006 Simulation Report v1.0). Simulation assumptions were informed by pilot data and data from the Modius device as follows:

- 90Kg median baseline weight in both groups (log-normal distribution with CV=24%),
- 6.6% mean percent weight loss in the active group at 6 months (SD 3.9%),
- 3.1% mean percent weight loss in the control group at 6 months (SD 3.9%),
- correlation between baseline weight and weight loss at 6 months of 0.4.

Under these assumptions, with a sample size of 180 participants randomized 1:1 active: placebo, there is greater than 80% power to demonstrate both the weight loss mean and categorical acceptance criteria at the 6 month time point.

Under an assumption of no difference between active and control but the same assumptions around SDs and correlations there is <2% probability overall of a type-I error with this sample-size.

Anticipating a drop-out rate of 10%, we will plan to recruit n = 200 total subjects overall in the study across all sites.

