## Neurovalens Limited

Clinical Study Identifier: 243973

Identifier: EXP18020

The multiple imputation method will be considered primary, with the analyses using LOCF and BOCF imputation considered supportive. These methods will be applied to missing data at 6 months and also at 3 months for use in the repeated measures model. A separate multiple imputation model will be fitted for each time point.

For the binary weight loss endpoint, subjects who have missing data and withdrew due to adverse events or a change in medication will be considered non-responders in all analyses. Other subjects with missing data will use their imputed weight value to determine response status.

Additionally, a sensitivity analysis will be performed with the binary weight loss endpoint. This analysis will include a best-case scenario, assuming subjects with missing values (and that did not withdraw due to adverse events or change in medication) have all lost over 5% body weight if randomized to VeSTAL device and not lost over 5% body weight if randomized to sham control, and a worst-case scenario, assuming no such subjects with missing values have lost over 5% body weight if randomized to VeSTAL device and all lost over 5% body weight if randomized to sham control. If the best and worst case scenario imputations provide conflicting conclusions i.e. straddle p=0.05 then a tipping point analysis will be used to determine the proportion of values imputed with the best or worst case scenario at which the level of imputation changes the significance of the binary weight loss criterion (as described in Yan et al., 2009).

For adverse events which have missing or partial start dates, and it is unclear as to whether the AE (or ADE) is treatment emergent, the worse-case scenario will be assumed to categorise the AE (or ADE) as treatment emergent.

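### The US responder verdict is read from one of 75 imputed datasets, so its 95% interval is too narrow and pass or fail can change with the imputation seed

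*SAP*

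**What the plan says.** SAP 2.3.1 lists two numerical criteria for US success. One requires: "The lower bound of the 95% confidence interval of the response rate in the VeSTAL device group exceeds 50" per cent. SAP 12.1.2 repeats it as a criterion for success, so the word supportive in that section's title does not demote it. The interval is a "two-sided 95% exact binomial confidence interval for the response rate", in line with Protocol 34.1.

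On missing data, 12.1.2 says: "The analysis will use the multiple imputation for missing data as primary", with LOCF and BOCF as supportive. SAP 10.2 fixes subjects with missing data who withdrew for adverse events or a medication change as non-responders. For the rest: "Other subjects with missing data will use their imputed weight value to determine response status".

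For the multiple-imputation analysis, 12.1.2 takes the median of the between-arm Fisher p-values and then adds that "the exact confidence intervals described above will be produced using the imputation with a p-value equal to or nearest the median p-value". The step in 10.2 that combines the 75 analyses is written for body weight loss as a continuous endpoint. Neither section gives a pooled response rate, a pooled interval, a tie-break or a seed.

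**The concern.** Imputing 75 times lets the spread between datasets carry the uncertainty about the missing values. An interval computed in one completed dataset discards that spread and treats imputed responders as known. This is a gap in the plan rather than a contradiction: the continuous endpoint is pooled and this criterion is not.

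The selector also does not match the criterion. The Fisher p-value compares two arms, while the criterion uses the active arm alone, so noise in the sham imputations helps decide which active count is judged. The other 74 datasets influence which dataset is picked, but contribute nothing to the interval's width.

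This is one of the two criteria on which the US claim rests, and with 100 subjects per arm the exact rule turns on a single responder.

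**Working it through.** **Inputs.** SAP section 5: 180 evaluable subjects 1:1, 200 recruited, 10% dropout, mean loss 6.6% against 3.1%, SD 3.9%, baseline weight log-normal with median 90 kg and CV 24%, correlation of size 0.4 with baseline weight. (The protocol gives the correlation a negative sign; this does not alter the residual SD.) SAP 10.2: 75 imputations by regression on treatment, gender and baseline weight.

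**The plan's own figures.** Recruitment reproduces: 180/0.9 = 200. The implied active response rate is Φ((6.6 − 5)/3.9) = 65.9%. With 90 per arm the exact rule needs 55 responders, with power 85.8%. The stated power above 80% for both criteria does not reproduce jointly when the mean criterion requires a lower limit above 2% (72.8%). That is a separate matter and is not used here.

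**Cut-off at 100 per arm.** The exact lower limit is the 2.5% quantile of Beta(x, n − x + 1): 60/100 gives 49.7% (fail) and 61/100 gives 50.7% (pass).

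**Ties.** Out of 100 per arm, 61 active against 40 sham and 60 against 39 have the same Fisher p-value, 0.00456. The first passes and the second fails, and the SAP has no rule for choosing between them.

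**Omitted variance.** With W the within-imputation variance and B the between-imputation variance, Rubin's total is T = W + (1 + 1/75)B. The interval uses W only, so the standard error is understated by 1 − √(W/T).

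**Simulation.** 100 per arm, the inputs above, weights missing completely at random, proper regression imputation, each trial imputed twice with independent seeds. There were 20,000 trials per scenario at the design effect, and 20,000 to 70,000 at a true 50% rate. The pooled comparator is an exact interval at effective sample size q(1 − q)/T, where q is the mean rate over the 75 datasets. The first column is the share of subjects whose weight is actually imputed.

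| Imputed | √(T/W) | SE understated | Seed flips, SAP / pooled | Power, SAP / pooled | False success at 50%, SAP / pooled |
|---|---|---|---|---|---|
| 5% | 1.023 | 2.2% | 3.3% / 0.8% | 86.5% / 86.9% | 2.0% / 1.8% |
| 10% | 1.048 | 4.6% | 5.4% / 1.1% | 86.4% / 85.5% | 2.2% / 1.6% |
| 20% | 1.101 | 9.2% | 8.0% / 1.8% | 84.9% / 82.1% | 2.7% / 1.4% |
| 30% | 1.161 | 13.9% | 10.6% / 2.8% | 83.5% / 77.1% | 3.2% / 1.0% |

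The mean lower limit is 55.8% under the SAP rule against 55.2% pooled at 10% imputed, and 55.7% against 54.6% at 20%.

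**Many seeds per trial.** At the design effect with 10% missing, the SAP verdict was not constant over 40 seeds in 20.1% of trials, against 3.3% when pooled.

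**Worked examples.** One simulated dataset each, 90 active subjects observed and 10 imputed, 400 seeds. The pooled limit is the Beta quantile above with n = 100/(T/W) and x = qn.

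| Observed responders of 90 | Seeds passing, SAP rule | Mean rate q | √(T/W) | Effective n | Pooled lower limit |
|---|---|---|---|---|---|
| 53 | 24% | 59.4% | 1.046 | 91.4 | 48.7% |
| 54 | 42% | 60.3% | 1.049 | 90.9 | 49.5% |
| 55 | 81% | 61.8% | 1.042 | 92.1 | 51.0% |
| 56 | 98% | 62.9% | 1.042 | 92.1 | 52.2% |

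In these four datasets the pooled rule fails the first two and passes the last two under essentially every seed (0%, 0.25%, 100% and 100% of seeds passing).

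**The case against.** The strongest reply is that little harm reaches the US claim. Success also needs the mean criterion, so a responder flip matters only when that criterion passes. In a 6,000-trial simulation at 10% imputed, the whole US verdict flipped with the seed in 4.2% of trials under the SAP rule and 1.7% under pooling. A properly pooled mean criterion alone flipped in 1.4%, so some seed dependence is normal with 75 imputations. US pass rates barely differ: 72.3% against 72.0% at 10% imputed, and 68.2% against 66.9% at 20%. False success at the planned 10% is below 2.5% because the exact interval is conservative, and the pooled exact interval is more conservative still. Withdrawals fixed as non-responders are not imputed, so 10% imputed is an upper case if total missingness is 10%. LOCF, BOCF, best- and worst-case analyses and, if those two conflict, a tipping point are planned and would expose a fragile result.

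All of this stands as a limit on size. It does not remove the defect. The joint verdict is still more than twice as seed-dependent as under pooling, and the sensitivity analyses do not correct the primary interval. Stating a seed would make the result repeatable, but the choice of dataset would remain arbitrary and the interval too narrow.

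**Conclusion.** The concern holds. As written, the primary interval for a criterion that decides US success omits between-imputation variance, and its verdict depends on the seed when the result is near 61 of 100. At the planned 10%, the standard error is about 4.6% too small and a second seed flips the responder verdict in 5.4% of trials. No type I error inflation is claimed at that level. At 20% and 30% imputed, false success is about 2.7% and 3.2%, but those shares are assumptions with no basis in the documents. The figures also assume data missing completely at random and the SAP's design values. The rule should be changed before analysis; the size does not make the trial uninterpretable.

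**What to change.** In SAP 12.1.2, estimate the VeSTAL response rate in each of the 75 imputations, pool it by a prespecified rule, and compare the pooled lower 95% limit with 50%. A suitable rule is an exact binomial interval at effective sample size q(1 − q)/T. It keeps the protocol's exact method and reduces to the planned interval when nothing is missing. Rubin's rules on the logit scale are an alternative, but with nothing missing they would pass 60/100 (lower limit 50.1%), which the exact interval fails. Keep the median p-value only for the supportive Fisher test, and state the imputation seed.

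The cost is SAP wording and a small programming change. Power for this criterion becomes 85.5% instead of 86.4% at 10% imputed, and 82.1% instead of 84.9% at 20%. With logit pooling it is 87.6% and 84.5%.

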## 12.1.3 Secondary Efficacy Analyses

For both the *EU and USA regulatory clearance pathways*, secondary efficacy analyses will be performed to investigate the difference between treatment groups (using multiple imputation, LOCF and BOCF for missing data for weight outcomes, observed data for other outcomes) in:

- Mean percentage weight loss;
  - A t-test will be used to detect a statistically significant difference (p-value < 0.05)

     between the mean percentage weight loss per group (unadjusted analysis).
  - The mean percentage weight loss between groups, having accounted for covariates of interest and repeated measures over time. In order to do so, a mixed effect repeated measures (MMRM) model will be developed using percentage weight loss at 3 and 6 months) and controlling for the prespecified covariates of interest: gender and baseline weight. Subject will be included in the mixed effects model as a random effect with an unstructured covariance structure. If a convergent model cannot be achieved with an unstructured covariance, further covariance structures will be tested sequentially until a satisfactory model has been achieved.
  - Plot of the Ismeans of change from baseline at 3 and 6 months obtained from the MMRM analysis described above with MI for missing data only
- Adjusted response rate;
  - o whereby response is defined as a subject achieving a percentage weight loss of at least 5% by 6 months. The adjusted response rate will be obtained by means of a logistic regression model with a binary response indicator as the dependent variable, treatment group as the explanatory variable and adjusting for covariates of interest: gender and baseline weight.
- Mean percentage VAT loss;
  - Summary statistics for percentage VAT loss at 3 and 6 months from baseline by treatment group
  - o Plotted graphically by treatment group over time
  - A linear model will be used for the mean percentage VAT loss at 6 months having adjusted for covariates of interest: gender and baseline VAT. The least square (LS) mean difference between groups will be assessed for a statistically significantly difference from 0 i.e. p-value <0.05.

- Mean percentage fat loss;
  - Summary statistics for percentage fat loss at 3 and 6 months from baseline by treatment group
  - Plotted graphically by treatment group over time

Neurovalens Limited Identifier: EXP18020

Clinical Study Identifier: 243973

 A linear model will be used for the mean percentage fat loss at 6 months having adjusted for covariates of interest: gender and baseline weight. The least square (LS) mean difference between groups will be assessed for a statistically significantly difference from 0 i.e. p-value <0.05.

- Mean percentage change in lean muscle mass;
  - Summary statistics for percentage change in lean muscle mass at 6 months from baseline by treatment group
  - Plotted graphically by treatment group over time
  - A linear model will be used for the mean percentage change in lean muscle mass at 6 months having adjusted for covariates of interest: gender and baseline lean muscle mass. The least square (LS) mean difference between groups will be assessed for a statistically significantly difference from 0 i.e. p-value <0.05.

  - Additional fat and mass endpoints;
    - For each of the following endpoints, comparisons will be performed using a linear model, with the efficacy endpoint at 6 months as the dependent variable and treatment group, gender and baseline value as the explanatory variable.
       Data will also be summarised descriptively over time:
      - Mean percentage trunk fat loss
      - Mean percentage bone mineral content (BMC) gain
- Dietary endpoints;
  - Questionnaire responses, inclusive of those received via the food frequency questionnaire (FFQ) (baseline only) and the two-day 24-hour dietary recall will be summarized per treatment group at baseline and 6 months for the following endpoints:
    - Total Energy Intake (kCal)
    - Carbohydrates (Starchy carbohydrates, sugars and free sugars)
    - Fat and saturated fat
    - Protein
    - Fiber
    - Alcohol

Neurovalens Limited Identifier: EXP18020

Clinical Study Identifier: 243973

A statistical comparison will be performed between treatment groups for the change from baseline in the total calorie intake at 6 months, using a linear model, with the dietary endpoint as the dependent variable and treatment group, gender and baseline calorie intake as the explanatory variables. The two-day 24-hour dietary recall will be used to provide the total calorie intake data at the 6-month time point and baseline. Data will be summarised descriptively and plotted graphically over time.

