### 10.2 Premature Withdrawal and Missing Data

All subjects enrolled into the study who meet the requirements for the ITT or Safety Analysis Set population will be included in the final analyses. This will include those subjects who withdrew from the study prematurely or have missing data.

For the large part, subjects will contribute what data they have available without imputation. However, for the primary efficacy endpoint of total body weight loss, three approaches to missing or incomplete data will be taken, under the assumption that the data is missing at random:

- 1. Multiple imputation will be applied by means of a multiple imputation model which is composed of three steps:
  - 1.1. The missing data are imputed multiple times to generate multiple sets of data. The imputed values are predicted total body weight loss values obtained from a linear regression model with observed total body weight loss data as the dependent endpoint, and the same covariates of interest that are used to adjust the primary endpoint (treatment group, gender and baseline weight). By providing 75 imputations per missing value, the variability between imputed values represents the uncertainty over the missing value.
  - 1.2. The 75 complete datasets are analyzed using the planned statistical analysis as per section 12.1.1. The results from the 75 complete datasets are then combined to produce an estimate for the primary endpoint, which reflects the uncertainty due to the missing values.
- 2. Last Observation Carried Forward (LOCF) will be applied for all subjects without data, inclusive of those who have withdrawn from the trial and subjects who have not reached the time point.
- 3. Baseline Observation Carried Forward (BOCF) will be applied for all subjects without data, inclusive of those who have withdrawn from the trial and subjects who have not reached the time point.

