## 12.1.1 Primary Efficacy Analyses

As the primary efficacy endpoints differ between regulatory clearance pathways, the primary efficacy analyses also differ accordingly.

For both the *EU and USA regulatory clearance pathways*, the primary efficacy endpoint will be summarized using summary statistics for the percentage weight loss at the 6 month time point. The mean percentage weight loss will also be presented graphically, by treatment group, over time. Summaries and graphical outputs will be produced for observed data unless specified otherwise..

For the continuous efficacy endpoint, mean percentage weight loss at 6 months, the difference between treatment groups will be assessed using a linear model controlling for covariates of interest: gender and baseline weight. The least square (LS) mean difference between groups will be assessed for a statistically significantly difference from 0 i.e. p-value <0.05. For the USA regulatory clearance pathway, the lower limit of the confidence interval of the LS Mean difference between groups will be assessed against the 2% target for a successful study, whereas the EU regulatory clearance pathway will assess whether the LS mean difference between groups is significantly different from zero. Analysis using multiple imputation for missing data will be primary, with the LOCF and BOCF imputation methods used for supportive analyses.

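### The repeated-measures model is fitted only to already-imputed weights, so at month 6 it repeats the linear model and adds no check on dropout

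*SAP*

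**What the plan says.** SAP section 12.1.3 lists a repeated-measures model of percentage weight loss at 3 and 6 months, adjusted for gender and baseline weight, with unstructured covariance. It falls under a rule for the whole section: "using multiple imputation, LOCF and BOCF for missing data for weight outcomes", while non-weight outcomes are analysed as observed. The LS-mean plot is taken from the MI version only.

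SAP section 10.2 leaves no doubt that imputation comes first: "These methods will be applied to missing data at 6 months and also at 3 months for use in the repeated measures model". It adds: "A separate multiple imputation model will be fitted for each time point". The predictors in each imputation model are treatment, gender and baseline weight, and 75 datasets are produced.

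The primary analysis in SAP section 12.1.1 is "a linear model controlling for covariates of interest: gender and baseline weight", with MI primary and LOCF and BOCF supportive. SAP section 4 calls LOCF and BOCF sensitivity methods. The best-case, worst-case and tipping-point analyses concern only the 5% responder endpoint.

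Protocol section 34.1 says "we will use a linear mixed effects model for weight over time", with a time-by-group term and a random intercept. It does not say that the weights are imputed beforehand, and SAP section 13 does not list this as a change.

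**The concern.** A repeated-measures model helps with dropout because a subject seen at month 3 but not at month 6 still contributes. By likelihood, the observed month-3 weight informs the missing month-6 weight. Filling both visits first removes that use. The separate MI models do not restore it, because month-3 weight is not a predictor of month-6 weight. LOCF does carry the month-3 value forward, but only by assuming no change after month 3.

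The planned results would show a month-6 difference from the linear model and another from the repeated-measures model, for each of MI, LOCF and BOCF. A reader could take agreement within each pair as evidence that dropout does not matter, when it follows from the algebra. The analysis that would use the month-3 weights of later dropouts under missing at random is not in the plan.

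**Working it through.** **1. The plan's own figure.** The only stated dropout figure is 10%: 180 / (1 − 0.10) = 200, which reproduces. The SAP gives no figure for the repeated-measures model.

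**2. Algebra.** Let X hold intercept, treatment, gender and baseline weight for all n subjects. Let Y3 and Y6 be the completed outcomes, and Σ the 2×2 within-subject covariance. With every term crossed with visit, the design is I ⊗ X, and generalised least squares gives

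β = (Σ⁻¹ ⊗ X′X)⁻¹ (Σ⁻¹ ⊗ X′) Y = (I ⊗ (X′X)⁻¹X′) Y.

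Σ cancels. The month-6 part is (X′X)⁻¹X′Y6, which is the section 12.1.1 linear model. This holds in each imputed dataset, so it holds after pooling, and equally for LOCF and BOCF. With unstructured covariance the REML month-6 variance is RSS/(n − p), so the standard error matches too.

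**3. Numerical check.**
- Inputs from SAP section 5: 6.6% v 3.1%, SD 3.9, n = 200, baseline correlation 0.4 in size.
- Assumed: month-3 loss 4.0 v 2.0, SD 3.0; month-3/month-6 residual correlation 0.7 or 0.85; 30% male; a quarter of dropout before month 3 at random, the rest driven by month-3 loss.
- Runs: 60 trials per scenario, with 75 imputations in the first three and 20 in the rest.

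One simulated trial (full-data estimate 3.624):

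| Data | Linear model | Repeated measures, crossed terms |
|---|---|---|
| MI | 3.547 (SE 0.469) | 3.547 (SE 0.469) |
| LOCF | 3.213 | 3.213 |
| BOCF | 2.837 | 2.837 |
| Observed, no imputation | not planned | 3.621 (SE 0.473), not planned |

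Over all trials the largest gap between the two models was 3e-14 (MI estimate), 1e-8 (MI standard error) and 3e-13 (LOCF and BOCF estimates). With gender and baseline weight as main effects only, but treatment-by-visit kept, the mean absolute gap under MI was 0.03 to 0.04 points (largest 0.27). That gap reflects covariate imbalance, not dropout: at 10% dropout for opposite reasons, the two models departed from the full-data result by +0.522 and +0.516.

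**4. What an observed-data fit would add.** When subjects leave after month 3, the likelihood estimate is approximately

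d6(completers) + b × [d3(all) − d3(completers)],

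where d is the treatment difference and b the slope of month 6 on month 3. Per-visit MI returns d6(completers) on average. At correlation 0.8, b ≈ 0.8 × 3.9 / 3.0 = 1.04, so a distortion of the month-3 difference among completers carries over almost one for one.

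Mean departure from the full-data difference (step 3 inputs):

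| Dropout | Correlation | Reason for leaving | MI | Observed-data model | LOCF | BOCF |
|---|---|---|---|---|---|---|
| 10% | 0.7 | same in both arms | +0.01 | 0.00 | −0.20 | −0.36 |
| 10% | 0.7 | opposite by arm | +0.52 | +0.02 | −0.23 | +0.12 |
| 10% | 0.85 | opposite by arm | +0.62 | +0.01 | −0.13 | +0.21 |
| 20% | 0.7 | opposite by arm | +0.93 | +0.02 | −0.44 | +0.11 |
| 30% | 0.7 | same in both arms | +0.07 | +0.01 | −0.55 | −0.94 |
| 30% | 0.7 | opposite by arm | +1.24 | +0.02 | −0.59 | +0.07 |

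MI, LOCF and BOCF are the linear-model results. Opposite means that poor month-3 losers leave VeSTAL and good ones leave sham. Selection was set stronger there (1.5 v 1.0 per SD on the log scale), so the contrast with the same-reason rows is not purely one of direction.

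A second set-up assumed month-3 means 4.4/2.1, SD 3.0 and correlation 0.8. It let 15% of VeSTAL leave, mainly poor month-3 losers, and 5% of sham at random, which is 10% overall. Selection strength is a free choice here. Four runs gave:

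| Full data | MI | LOCF | BOCF | Observed-data model | MI − full |
|---|---|---|---|---|---|
| 3.50 | 3.93 | – | – | 3.50 | 0.43 |
| 3.49 | 3.92 | 3.23 | 3.10 | 3.49 | 0.43 |
| 3.49 | 3.99 | 3.23 | 3.16 | 3.49 | 0.50 |
| 3.53 | 4.11 | 3.27 | 3.27 | 3.53 | 0.58 |

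**The case against.** **A reader might infer that the plan would confirm dropout bias and never expose it.** The documents do not support that. LOCF and BOCF linear models stand beside the primary MI analysis, and in the second set-up they fall about 0.7 to 0.8 points or more below MI (3.92 v 3.23; 4.11 v 3.27). That split would be a warning. What stands is narrower: neither recovers the full-data value there, neither assumes missing at random in a way that uses both visits, and their repeated-measures versions only repeat them.

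**A reader might infer an exact copy.** The SAP does not state covariate-by-visit terms, or even treatment-by-visit, although plotting LS means at both visits implies the latter. Exact identity needs the crossed terms. Without them the results are close but not equal.

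**A reader might blame the 0.4 to 0.6 points on the repeated-measures model.** They arise because the MI model leaves out month-3 weight, which is a matter for the primary analysis. Adding it there would help the primary estimate, though a repeated-measures fit to those completed data would still repeat the linear model.

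**The model is not presented as a dropout check.** The protocol gives its purpose as longitudinal, the SAP does not name it a sensitivity analysis, and it supplies month-3 estimates that the primary model does not. That is fair. No success criterion or label claim uses it.

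**Conclusion.** The point holds in limited form. As written, the repeated-measures model gives essentially no month-6 information beyond the linear model under the same imputation, and it does not use observed month-3 weights to inform missing month-6 weights. The equality is exact with crossed covariates and near (about 0.04 points on average) with main effects. This part needs no dropout assumption.

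The size of what is missed does rest on assumptions, because the documents give no month-3 means, no between-visit correlation and no dropout pattern. If leaving depends on month-3 loss differently by arm, at about 10% overall, the planned MI is off by roughly 0.4 to 0.6 points and an observed-data model by 0.02 or less. With the same reason in both arms, MI is off by 0.01 at 10% dropout and 0.07 at 30%.

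For scale, with 90 per arm and the SAP's inputs the adjusted standard error is 3.9 × √(1 − 0.4²) × √(2/90) = 0.533. The expected lower 95% limit is then 3.5 − 1.96 × 0.533 = 2.46, or 0.46 above the 2% USA target. A departure of that order would matter to interpretation, so a model that can show it is worth having.

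**What to change.** In SAP sections 12.1.3 and 10.2, fit the repeated-measures model to the observed 3- and 6-month percentage weight loss with no prior imputation. Cross treatment, gender and baseline weight each with visit, and use unstructured covariance. Report the month-6 difference with its 95% CI, and base the LS-mean plot on this fit. The MI, LOCF and BOCF versions may be kept, with a statement that they are not independent support for the linear-model results under the same imputation.

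The cost is SAP wording and one model fit. No new data are needed and the primary analysis is untouched. Subjects with no post-baseline weight do not contribute to this secondary model, although they remain in the primary MI analysis. The model still assumes missing at random, so it does not replace a missing-not-at-random analysis of the continuous endpoint.
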